4.2.6 Exploratory

- Patient questionnaire

Number (%) of patients falling in each questionnaire category will be presented.

RAASi dose change related variables

Baseline RAASi user will be determined based on the information collected on CRF (CM module). A patient is considered to be on RAASi, if (s)he used RAASi on the day of first CP dose (Day1) of ZS.

RAASi use at end of treatment will be determined based on the information collected on CRF (CM module). Patients are regarded as discontinued RAASi, if (s)he is no longer on RAASi at the end of treatment (last ZS dose date).

During the study, any dose change of RAASi will be recorded on the separate CRF module (RAASIT), with the corresponding reason for changes. While it is anticipated there will be various pattern of RAASi changes, investigators are guided to choose either of “increase”, “decrease” or “no change”, *relative to previous RAASi intensity*, based on whether their intention of treatment change was to intensify, to diminish, or neither.

Table 6 RAASi dose changes

For	Variable	Condition
Baseline RAASi user	Subjects who discontinued RAASi	- No RAASi medication at the end of ZS treatment
Baseline RAASi user	Subjects who increased RAASi doses	- at least one dose increase events - no dose decrease events
Baseline RAASi user	Subjects who decreased/discontinued RAASi doses	- at least one dose decrease events - no dose increase events
Baseline RAASi user	Subjects who did not change RAASi intensity	- no records of “increase” or “decrease” events during study.
Baseline RAASi user	Subjects who increased at least once RAASi due to each reason	at least one cause-specific increase events (e.g. “titration”) regardless of trajectory of RAASi changes before or after that increase.

Table 6 RAASi dose changes

For	Variable	Condition
Baseline RAASi user	Subjects who at least once decreased/discontinued due to each reason	
 - at least one cause-specific decrease events (e.g. “high potassium”) - regardless of trajectory of RAASi changes before or after that decrease
Baseline RAASi non-user	Subject who initiated RAASi	
 - at least one dose increase events - regardless of the trajectory of after that dose increase

For each of above category, proportion of subjects will be calculated.

Further, time to first reduction/discontinuation of RAASi will be presented with Kaplan Meier plot for baseline RAASi user. Subjects will be censored at the last day of ZS dose.

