Throughout all phases of the study, most potassium values will be measured at fasting before taking ZS. Nothing should be taken by mouth except water, coffee or tea, with or without milk and/or sugar, and essential medications, for a minimum of 8 hours prior to the blood collection. Potassium level should be determined by both i-STAT and the Central Laboratory on all occasions. Treatment decisions (eg, dose titration, stopping rules) will be made based on

i-STAT potassium values, as these provide clinical sites with a real-time measurement, according to dose modification rules. Statistical analyses on the study data will in principle be based on S-K values as measured by the Central Laboratory.

Safety and tolerability will be assessed on an ongoing basis. Standard study assessments including blood potassium, clinical chemistry (including calcium, magnesium, sodium, phosphate, creatinine, bicarbonate, and blood urea nitrogen [BUN]), aldosterone, renin and hematology parameters, urinalysis, vital signs, physical examinations, and electrocardiograms (ECGs) will be assessed. All women of childbearing potential will have a urine pregnancy test prior to enrollment and at their End of Study (EOS) visit.

Stopping rules will be implemented to ensure subjects discontinue the study treatment and receive alternative therapy in case of significant hyperkalemia, hypokalemia, arrhythmias, or development of congestive heart failure or end stage renal failure.

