4.1.4 Last on-treatment

The last on-treatment value is defined as the last measurements taken within 1 day (2 days, on QOD regimen) after last ZS dose (scheduled or unscheduled). For by-visit summary, the last on-treatment measurement during the respective phase will be additionally displayed.

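### RAASi observation in SAP 4.2.6 ends on the last ZS dose date, so a first RAASi cut made at a visit that ends ZS early is lost from the Kaplan-Meier plot although other Table 6 rows can count it

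*SAP*

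**What the plan says.** Two RAASi outputs in SAP 4.2.6 are tied to the last ZS dose date.

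- Kaplan-Meier plot of time to first reduction or discontinuation: "Subjects will be censored at the last day of ZS dose".
- Discontinuation status: "Patients are regarded as discontinued RAASi, if (s)he is no longer on RAASi at the end of treatment (last ZS dose date". The matching Table 6 condition is "No RAASi medication at the end of ZS treatment".

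The other Table 6 rows work differently. Under 4.2.6, "any dose change of RAASi will be recorded on the separate CRF module (RAASIT"), with a reason. The row for decreased or discontinued doses requires "at least one dose decrease events" and no increase. The by-reason rows need one cause-specific event. None of them states a last-dose cut-off.

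On timing, section 1.2 says that "most potassium values will be measured at fasting before taking ZS". It also says "Treatment decisions (eg, dose titration, stopping rules) will be made based on" the i-STAT value, which sites have in real time.

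For other data the SAP uses a short window after the last dose. Section 4.1.4 defines the last on-treatment value as "the last measurements taken within 1 day (2 days, on QOD regimen) after last ZS dose". The same window of 1 day (2 on QOD) applies to serum potassium and the Visit 23 limit (4.1.3), the i-STAT sensitivity analysis (4.2.4.1) and treatment-emergent adverse events (4.2.7.1).

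**The concern.** If the blood draw comes before the day's dose and ZS is stopped on the result, the last dose lies before the visit. A RAASi change ordered at that visit then falls after the end of RAASi observation, although the potassium value that prompted it counts as on-treatment.

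The loss runs one way. Events can only be removed, so the plot can only look better than what happened. The censoring may also be informative: high potassium is one ground for stopping ZS, and 4.2.6 itself gives it as an example reason for a RAASi decrease. The exploratory objective in 1.1 is to describe RAASi changes and their reasons over the treatment period. A reader of the plot would want to know whether RAASi was cut at the visit where ZS ended.

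**Working it through.** **Date logic.** Let ZS be stopped at a pre-dose visit on day d. The last ZS dose is d − 1 on QD and as early as d − 2 on QOD. A RAASi change dated d is later than the cut-off in both cases. With the SAP's window the end of observation is (d − 1) + 1 = d on QD. On QOD it is (d − 2) + 2 = d. The change is then included.

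**Worked case (constructed).** A baseline RAASi user on QD has no earlier RAASi change. The pre-dose i-STAT value at the MP Day 110 visit leads to ZS being stopped, and RAASi is stopped that day for high potassium. The last ZS dose is Day 109.

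| Output | Rule | Result |
|---|---|---|
| Serum potassium on Day 110 | last dose + 1 day = Day 110 | on-treatment |
| Adverse event with onset on Day 110 | last dose + 1 day = Day 110 | treatment-emergent |
| Kaplan-Meier plot | censored on Day 109 | no event |
| Discontinued RAASi (status) | status on Day 109 | still on RAASi |
| Decreased or discontinued doses | RAASIT decrease record, no cut-off stated | can count |
| Decreased or discontinued, by reason | RAASIT record with reason, no cut-off stated | can count |

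The last four rows all come from 4.2.6 and disagree about the same subject. Had the dose only been reduced, the status row would be unaffected, because the subject is still on RAASi under any window.

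**Tie.** If ZS was taken on the visit day, the RAASi change and the censoring share a date. The usual Kaplan-Meier convention counts the event, but the SAP states no rule. The status row could still read as on RAASi if RAASi was also taken that day, by analogy with the SAP's baseline rule.

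**Size.** The SAP gives no figure for the RAASi analysis. Its only related input is the 35% drop-out in 1.3. That sample-size statement reproduces approximately: 100 / 0.65 = 153.8, or 154, against 150 stated; 150 × 0.65 = 97.5. Drop-outs would be 150 × 0.35 = 52.5. How many are RAASi users is not given.

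An illustration of the mechanism needs two assumed inputs: b, the 52-week risk of a first RAASi reduction apart from ZS-ending visits, and q, the share of early ZS stops with a RAASi cut at the same visit. With constant hazards and all of the 35% treated as early ZS stops decided at a visit:

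- cut-off at last dose: risk shown = b
- with the window: risk = 1 − (1 − b) × 0.65^q

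| b | cut-off at last dose | q = 0.10 | q = 0.25 | q = 0.50 |
|---|---|---|---|---|
| 5% | 5% | 9.0% | 14.7% | 23.4% |
| 10% | 10% | 13.8% | 19.2% | 27.4% |
| 20% | 20% | 23.4% | 28.2% | 35.5% |

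For b = 10% and q = 0.25: 1 − 0.90 × 0.65^0.25 = 1 − 0.90 × 0.898 = 19.2%. A simulation of 20,000 subjects on the Table 3 visit days agreed within about one percentage point (for this cell, 9.9% without and 19.2% with the window). It counted no visit-day cuts under the current cut-off. That zero follows from setting the last dose to the day before the visit, so it confirms the date logic and is not evidence on frequency.

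**The case against.** The strongest reply is that the cut-off is a choice of estimand. The objective in 1.1 is confined to the treatment period, 4.2.6 uses the last dose date in both places, and exposure in 4.2.3.1 also ends there. A RAASi cut made as ZS is withdrawn may be precautionary and need not show that RAASi could not be kept on ZS. The window in 4.1.3, 4.1.4 and 4.2.7.1 is written for measurements and adverse-event onset, not for treatment decisions. Only most potassium values are pre-dose.

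Much of this stands. Ending at the treatment period is legitimate. What remains is that the SAP elsewhere treats the visit one or two days after the last dose as on-treatment, and that outputs within 4.2.6 can contradict each other.

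Three stronger readings are tempting and not supported:

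- *The RAASi cut is counted nowhere.* The RAASIT-based rows of Table 6 state no last-dose cut-off and can count it with its reason.
- *The rule drops the cuts most closely tied to ZS failure.* In the Maintenance Phase, Table 1 ends ZS for high potassium only above 6.5 mmol/L; from 5.1 to 6.5 the dose is raised, or kept at 15 g. Its other stops are for low potassium. A value of 5.1 or more on Correction Phase Day 4 also ends treatment (1.2), but 4.2.6 does not say whether those subjects enter the analysis. Overlap between ZS stops and RAASi cuts is plausible, not shown.
- *A definite number of subjects is misclassified.* The 35% is an all-cause planning figure without reasons or timing. Any same-visit share or number of RAASi users would be assumed. Subjects with an earlier reduction lose nothing, and reductions never enter the discontinuation row.

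A blanket window has a fault of its own: it would bring in completers' changes at Day 362, some made in anticipation of the planned end of ZS.

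**Conclusion.** The point holds in a limited form, with minor severity. For subjects whose ZS ends early at a pre-dose visit, a first RAASi reduction or stop made at that visit is lost from the Kaplan-Meier plot, and a stop is also lost from the status row. Both errors favour apparent RAASi persistence, and the RAASIT-based rows can show the opposite for the same subject.

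This rests on the last dose preceding the stopping visit, which section 1.2 makes normal but not universal. The amount of bias cannot be derived from the SAP; the table above shows how it would move under assumed inputs and is no estimate for this trial. The analysis is exploratory, and 4.1.1 says there is no confirmatory testing, so no main conclusion of the study depends on it.

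**What to change.** In 4.2.6:

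- For subjects who stop ZS early, end RAASi observation at last ZS dose + 1 day (+ 2 days on QOD), for both the Kaplan-Meier censoring and the end-of-treatment status.
- State that a RAASi change dated on the censoring day is an event, and that a RAASi stop dated on that day counts as off RAASi in the status row.
- For completers, keep changes made at the Day 362 visit out of the main curve and report them separately by recorded reason.
- State which cut-off applies to the RAASIT-based rows of Table 6, so that all RAASi outputs cover the same period.

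Following RAASi to the EOS visit in early stoppers is optional, since it goes beyond the treatment-period objective. The window will not capture subjects who stopped taking ZS several days before the visit.

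The cost is SAP wording and a changed date rule in the program; the CM and RAASIT records are already collected. Reported persistence may be slightly less favourable, and completers need one extra line of output.

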4.2.7 Safety

4.2.7.1 Adverse events

Adverse events will be classified by the Medical Dictionary for Regulatory Activities (MedDRA). Adverse events will be considered Treatment-Emergent if onset is on or after first dose of ZS and on or before last dose of ZS + 1 day (+ 2days, on QOD regimen). AEs starting before 1st AEs with onset during correction phase and those with onset during maintenance phase will be separately summarized, unless otherwise specified. Adverse events starting before first dose of ZS or more than 1 day (+2days, on QOD regimen) after last dose of ZS will only be listed.

All Adverse events (including SAEs)

Summary of following TEAEs will be separately presented for Correction Phase as well as for Maintenance Phase by SOC and PT. Number and proportion of subjects with these events as well as the events rates will be provided.

- Most common AEs (i.e. reported by $\geq 2\%$ of patients based on Preferred Term)
- Any AEs
- Deaths
- Serious AEs (SAEs)
- AEs leading to drug discontinuation (DAEs)
- AEs by maximal intensity

- AEs related to study drug

In addition, incidence of AEs by MP study period (Day 1-7, Day 8-30, Day 31-90, Day 91-180, Day 181-270, Day 271-360, After Day 360) will be presented.

Adverse events of special interest (AEOSI)

Oedema-related events

Oedema related event will be defined as any of the following events (PT): Fluid overload, Fluid retention, Generalised oedema, Hypervolaemia, Localised oedema, Oedema, Oedema peripheral and Peripheral swelling.

Cardiac Failure

Cardiac Failure will be searched by SMQ “Cardiac Failure” (narrow).

Hypertension

Hypertension will be searched by SMQ “Hypertension” (narrow).

Treatment-emergent Oedema-related events, Cardiac Failure and Hypertension will be summarized by PT using as number (%) of subjects with events as well as exposure corrected event rates.

Subgroup analysis of Adverse Events

Any treatment-emergent AEs stratified by age (<65, >= 65 years, <75, >= 75 years), gender, comorbidities (HF, CKD and DM), use of medications (RAASi and Diuretics), baseline S-K (<5.5, 5.5-<6.0, >= 6.0 mmol/L), baseline eGFR (<30, 30-< 60, >= 60 mL/min/1.73m²) and baseline weight (<65, >= 65kg) will be provided by SOC and PT.

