1. STUDY DETAILS

1.1 Study objectives

Primary Objective:	Outcome Measure:
Maintenance Phase To assess open-label, long-term (12 months) safety and tolerability for ZS in Japanese subjects with hyperkalemia (serum potassium ≥ 5.1 mmol/L).	Safety and tolerability as measured by adverse events reporting, vital signs, ECGs, physical examinations, and safety laboratory measurements.

Secondary Objectives:	Outcome Measures:
Maintenance Phase 
 To evaluate the proportion of ZS-treated subjects in whom normokalemia can be maintained over prolonged periods of time, using an individually titrated dose (5 g every other day [or 2.5 g once daily], 5 g once daily, 10 g once daily or 15 g once daily) To explore the time course of S-Aldosterone and S-Bicarbonate 	
 Proportion of patients who can maintain normokalemia (defined as S-K level of ≥ 3.5 and ≤ 5.0 mmol/L, inclusive) on ZS at each Maintenance Phase study visit Proportion of patients with average S-K ≤ 5.1 mmol/L Proportion of patients with average S-K ≤ 5.5 mmol/L Proportions of patients who were normokalemic (S-K ≥ 3.5 and ≤ 5.0 mmol/L), hypokalemic (< 3.5 mmol/L), or hyperkalemic (> 5.0 mmol/L) at each Maintenance Phase visit. Subject-level average S-K over certain period of time Observed values at visit and change from baseline in S-K over time Number of normokalemic days during Maintenance Phase Change in S-K level from the last on-treatment Maintenance Phase visit to the End of Study (EOS) Change from baseline in S-Aldosterone over time Proportion of patients with normal S-Aldosterone Change from baseline in S-Bicarbonate Proportion of patients with normal S-Bicarbonate

Secondary Objectives:	Outcome Measures:

 To evaluate the health state in the study population using SF-36 v2. 	
 SF-36 v2 questionnaire

Correction Phase To assess efficacy, safety and tolerability of 10 g TID ZS in Japanese patients with hyperkalemia (serum potassium [S-K] \geq 5.1 mmol/L).
	
 Observed values and change from Correction Phase baseline in S-K Proportion of patients who achieved normokalemia at 24, 48 and 72 hours after start of dosing Safety and tolerability as measured by adverse events reporting, vital signs, ECGs, physical examinations, and safety laboratory measurements during Correction Phase

Exploratory Objective:	Outcome Measure:

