4.2 Analysis methods

4.2.1 Study patients

4.2.1.1 Disposition of patients

The disposition of subjects for the enrollment period, correction phase treatment period, the maintenance phase treatment period and follow-up period will be summarized.

The summary of disposition for the enrolment period will include all Enrolled subjects (who signed informed consent).

The summary of disposition for correction phase will include SAF-CP. This summary will include subjects completing and discontinuing the correction phase treatment period.

The summary of disposition in the maintenance phase treatment will include SAF-MP. This summary will include subjects completing and discontinuing the maintenance treatment

period up-to Visit 17 (MP Day 194) and up-to Visit 23 (MP Day 362), broken down by reasons for discontinuation.

The summary of disposition in CP follow up period will include all subjects who discontinued correction phase or completed correction phase but did not enter MP. The summary of disposition in MP follow up period will include all subjects who discontinued or completed MP. For each, summary will include subjects completing and discontinuing the follow up period, broken down by reason for discontinuation.

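### Treatment-emergence and phase are set by AE onset alone: pre-dose AEs that worsen on ZS reach no summary table, and Maintenance Phase deaths or ZS stops from Correction Phase-onset AEs are counted only under the Correction Phase

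*SAP*

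**What the plan says.** Section 1.1 makes Maintenance Phase safety the primary objective: "To assess open-label, long-term (12 months) safety and tolerability for ZS in Japanese subjects". Section 3.2.3 evaluates the Correction Phase with the same safety variables.

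Section 4.2.7.1 then sets four rules.

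- **Treatment-emergence:** "Adverse events will be considered Treatment-Emergent if onset is on or after first dose of ZS and on or before last dose of ZS", extended by 1 day, or 2 days on the QOD regimen.
- **Phase:** "AEs with onset during correction phase and those with onset during maintenance phase will be separately summarized, unless otherwise specified".
- **Outside the window:** "Adverse events starting before first dose of ZS or more than 1 day (+2days, on QOD regimen) after last dose of ZS" are listed only.
- **Tables:** "Summary of following TEAEs will be separately presented for Correction Phase as well as for Maintenance Phase by SOC and PT". Deaths, SAEs, DAEs, maximal intensity and related AEs are items under that sentence.

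None of these rules refers to worsening, the date of death, the date an event became serious or the date ZS was stopped. The rider at the end of the phase rule allows exceptions, but none is given for these tables. The text just before the phase rule is also broken: "AEs starting before 1st AEs with onset during correction phase".

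For Maintenance Phase disposition on SAF-MP, section 4.2.1.1 says: "This summary will include subjects completing and discontinuing the maintenance treatment" period, broken down by reason. That summary does not depend on when an AE began.

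**The concern.** An onset date fixes where an event is counted for good, whatever happens to it later. That is harmless for a count of any AE. It matters more for deaths, serious events and discontinuations, which may come well after onset and which a reader will attribute to the treatment being taken at the time.

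Two groups are affected. The first is AEs that begin between consent and the first dose and become severe, serious or fatal on ZS; they enter no summary table in either phase. The second is AEs that begin in the Correction Phase and lead to death or a ZS stop in the Maintenance Phase. These are absent from the tables that answer the primary objective, and they appear as Correction Phase deaths or DAEs in subjects who completed that phase.

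The study has one arm and is descriptive (sections 1.2 and 4.1.1), so Maintenance Phase counts are read in absolute terms. The difference between no deaths and one death is a visible one. The same rules carry over to the interim analysis for regulatory submission (sections 5 and 8.1).

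**Working it through.** The SAP states no figure for this point, so the check applies its rules to each possible onset time and then sizes a single case.

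**Step 1. Where an outcome in the Maintenance Phase (MP) is reported**, under sections 4.2.7.1 and 4.2.1.1:

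| Onset of the AE | MP death/SAE/DAE tables | Correction Phase (CP) tables | Listing only | MP disposition, if ZS stops |
|---|---|---|---|---|
| In the MP | Yes | No | No | Yes |
| In the CP | No | Yes | No | Yes |
| Before first ZS dose | No | No | Yes | Yes |

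The second row is a matter of placement. The third row is a complete gap in the AE tables. In both, a subject who stops ZS in the MP because of the AE is in MP disposition but not in the MP DAE table. Maximal intensity follows the same pattern: an intensity reached in the MP is credited to the phase of onset, or to no table.

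**Step 2. How often the second row could arise.** Inputs: the CP lasts 1 to 3 days (section 1.2) and the MP runs to Day 362 (section 4.1.3). Assume a constant onset rate and full MP follow-up. The share of on-treatment onsets that fall in the CP is CP days / (CP days + MP days):

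- shortest CP: 1 / (1 + 362) = 0.28%
- longest CP: 3 / (3 + 362) = 0.82%

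Early stopping raises the share. With mean MP exposure halved to 181 days (illustration only), the upper figure is 3 / (3 + 181) = 1.63%. Only those CP-onset events that later end in death or a ZS stop in the MP are displaced. The frequency of pre-dose onsets cannot be derived from the SAP.

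**Step 3. What one case is worth.** Section 1.3 plans 150 enrolled subjects and at least 100 treated for a year, with 35% dropout. These figures agree to within about 3%: 100 / 0.65 = 153.8, and 150 × 0.65 = 97.5. The size of SAF-MP is not stated; 100 to 150 is assumed here. Exact 95% limits are Beta(0.025; x, n − x + 1) and Beta(0.975; x + 1, n − x), with a lower limit of 0 when x = 0:

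| SAF-MP (assumed) | Death counted in MP | Same death counted elsewhere |
|---|---|---|
| 150 | 1/150 = 0.67% (0.02 to 3.66%) | 0/150 = 0% (0 to 2.43%) |
| 100 | 1/100 = 1.00% (0.03 to 5.45%) | 0/100 = 0% (0 to 3.62%) |

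One displaced case therefore moves a Maintenance Phase proportion by 0.67 to 1.00 percentage point.

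**The case against.** The strongest reply is that onset allocation is a common and coherent convention, and that section 4.2.7.1 applies it consistently. Correction Phase-onset events are treatment-emergent and do appear in the Correction Phase tables; pre-dose events are at least listed; and disposition shows every Maintenance Phase stop with its reason. Whether a worsened AE is entered as a new AE with a new onset date is a recording rule usually left to the protocol, which was not available here. If it is entered that way, most of the worsening problem disappears. No confirmatory conclusion depends on the counts.

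Most of this stands, and it limits the point. A reader might infer that deaths, SAEs and discontinuations from earlier-onset events are lost from safety reporting. The SAP does not support that for Correction Phase onsets, which are tabulated in the other phase. Nor is the mismatch between DAEs and disposition a contradiction, because the two tables count different things. A material percentage undercount of Maintenance Phase DAEs cannot be claimed either, because the SAP gives no expected number. Oedema is an event of special interest, but the SAP says nothing of its timing and so does not make it a likely route.

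Two things survive. Recording worsening as a new AE would not move a death or ZS stop that arises from an earlier-onset AE with no new record. And nothing in the SAP brings a pre-dose AE that turns grave on ZS into any summary table. The broken sentence sits where such events might have been addressed, so the intended rule cannot be read from the text.

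**Conclusion.** The point holds in a limited form. As written, the SAP leaves pre-dose-onset AEs that worsen, become serious or are fatal on ZS out of every AE summary. It also counts Maintenance Phase deaths and ZS stops from Correction Phase-onset AEs only under the Correction Phase, so Maintenance Phase death and DAE counts may not agree with disposition.

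The expected number of cases is small: about 0.3% to 0.8% of on-treatment onsets fall in the Correction Phase under a constant onset rate and full follow-up, and only some of those lead to such an outcome later. Each case is worth about 0.7 to 1 percentage point if SAF-MP holds 100 to 150 subjects. Both ranges rest on assumptions that the SAP does not settle. The conclusion about pre-dose events also assumes that worsening is not already captured as a new AE. The change is worth making because the events concerned are the gravest in the primary safety assessment, not because many are expected.

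**What to change.** In section 4.2.7.1:

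1. Define treatment-emergent as onset, or worsening in intensity or seriousness, on or after the first ZS dose and within the existing on-treatment window. If worsening is already recorded as a new AE, say so instead.
2. Complete or delete the broken sentence before the phase rule.
3. Keep onset-based phase allocation for the standard AE tables.
4. Add Maintenance Phase counts of deaths by date of death and of AE-related ZS discontinuations by date of ZS stop, whatever the AE onset, and reconcile them to the disposition summary in section 4.2.1.1.

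The same additions should apply to the interim analysis. Moving SAEs between phases by the date they became serious is not proposed, because the SAP does not show that this date is collected; the seriousness part of item 1 likewise works only where the data show when the change occurred.

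The cost is a few lines of text and a small extra derivation. Maintenance Phase counts may rise slightly. The supplementary counts will not be strict subsets of the onset-based any-AE table, which a footnote should state.
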